2.9.2 Birth dose reporting form

To obtain information on the specifics of the birth dose administration, the reporting forms created for this pilot study will be used (Section 5.4). After each birth, a member of the maternity unit staff will fill out the birth dose reporting form, in addition to normal recording procedures. As part of the ongoing supervisory check-in the reporting forms will be sent through email or WhatsApp to study members for brief review. While data collectors are at each facility for registry extraction at end line, they will collect the completed birth dose reporting forms.

Contingency plan:

As the hard copy forms will be gathered at the end line of the study, in the event of worsening COVID-19 transmission, data collectors will delay collecting the birth dose reporting forms until it is safe to do so.

2.9.3 HCW surveys

To obtain HCW knowledge on birth dose vaccines and corresponding policies, we will conduct HCW surveys (Section 5.4). During the baseline, midline, and end line assessment, HCW's from the 15 facilities will be asked to participate in a survey over the phone with the intention to include a minimum of 3 HCW's from each facility. The survey is expected to take 1 hour and will consist of closed and open-ended questions. The baseline survey will be updated with appropriate language and indicators for the midline and end line survey. Telephone surveys will be scheduled at a time most convenient for the HCW. During the baseline assessment and before any surveys are conducted, copies of the consent form will be left at each facility for survey participants to read through. Prior to beginning the survey, we will read through the consent form to obtain verbal consent. The data collection team will conduct the surveys and will input the participant's survey responses on electronic tablets with all data to be stored on an encrypted server and accessed only by study team members.

Contingency plan:

In the event of worsening COVID-19 transmission and HCW's see a substantial increase in workload with no available time to complete the survey during working hours, surveys outside of working hours will be arranged. If this is required HCW's will be compensated for personal cell phone minutes.

2.10 Study Outcomes

The primary outcome of this pilot study is change in proportion of newborns receiving birth doses of BCG and OPVO within 24 hours. The key indicators from HCW surveys will be updated to include those from midline and end line surveys and will be sent for review prior to conducting those surveys.

Key Indicator	Source (data	Assessed at	Assessed at	Assessed
	collection tool)	baseline	midline	at end line
Average age of babies at time of	Birth registry and	×		×
receiving birth dose vaccines (BCG	immunization			
and OPV0)	record			
Proportion of babies born/received		×		×
in facilities receiving birth dose				
vaccines (BCG and OPV0) within 24				
hours				
The reason why BCG and OPV0 birth	Birth dose		×	×
dose vaccines were not administered	reporting form			
within 24 hours				
			×	×
			×	×
	HCW survey	×	×	×
Proportion of HCWs that know ideal		×	×	×
timing for birth dose vaccines				

Table 5. List of key indicators and sources

	×	×	×
Reported concerns with administering birth dose vaccines	×	×	×
within 24 hours			
Reported barriers to administering	×	×	×
birth dose vaccines within 24 hours			
Reported barriers to educating	×	×	×
caregivers on birth dose vaccines			
Maternity unit's access to birth dose	×	×	×
vaccines			

2.11 Data Analysis

All outcomes will be descriptive in nature with the intent to assess preliminary impact and not statistically significant findings. For both measures of timing of birth dose vaccines, we will compare the facility-level value at baseline to end line of the intervention. Basic statistics (means and proportions) will be performed on the HCW surveys and the new birth dose reporting forms. Information and recommendations reported in open-ended questions from HCW surveys may inform final recommendations of the project but only at an aggregated level and would not be published, shared, or reported at the individual level.

To identify indications of COVID-19 impacting in-facility births, we will use the information contained in the DHIS2 over the last 2 years to compare historical yearly birth trends for the 15 included facilities, with the trends we observed during this pilot study. Due to the small sample size of health facilities and short nature of this study any potential findings of changes in time trends will be descriptive in nature. During check-ins with the facilities the team will also document other factors due to the pandemic that may impact the study such as stock outs or changes on guidance. As this data is not formally gathered, this will be documented and descriptive in nature. Please refer to study tool "Notes for touch point calls" in Section 5.4 that will gather informal information about the health facility-specific processes.

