2.3 Study Period

The study is scheduled to take place for 20 weeks between January and April 2021.

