2.4 Study Population

The study population will include:

- All babies received in the maternity unit, or EPI unit for OPV0 and/or BCG vaccines in the 15 study facilities, during the 1-year baseline period and the intervention period;
- HCW from the 15 facilities involved in either EPI or maternity and newborn care

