Data extraction for children in the immunization register will occur by using a sampling interval to ensure children are sampled throughout the entire year. The sampling interval will be created by taking the total number of children entered into the immunization register for the previous 12 months and dividing by our required sample size (N = 30). For instance, if 90 children were entered into the register in the past 12 months, the sampling interval will be 3; if only 30 children were entered into the register in the past 12 months, the sampling interval will be 1. With the sampling interval, the data collector will count backwards from the most recent entry in the immunization register and begin gathering data. The data collector will record the name, date of birth, and record the date(s) of immunization for each of the birth vaccines in the immunization register. Using the name and date of birth, the data collector will then cross-check with the maternity registers to confirm that same child's date of birth. Records that are missing either a date of immunization or date of birth will be recorded to help determine how many children were potentially born out of the facility, or have incomplete records, but will not count towards the total desired sample size for timeliness coverage. Data collectors will continue working backwards through the registers entering data for every Xth child (according to the sampling interval) until they have successfully recorded the

date of immunization and date of birth for 30 children. If they reach the end of the year without entering complete data on 30 children, the data collector will be instructed to loop back through the year but start now on the second child registered when counting.

At end line:

The end line registry extraction will utilize the same sampling technique as baseline. The same sample size (N = 30) will be used with the sampling period being the duration of the study period.

Proportion of babies born in facilities receiving birth dose vaccines within 24 hours – Maternity registry extraction

At baseline:

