The same sampling interval/methodology described above will be utilized again, only this time the data collectors will begin with the birth registers to determine their sampling interval. Then this interval will be used to pull names first from the birth register to select a sampling of babies that were born in that specific facility and then cross-checked with immunization dates for birth vaccines in the immunization registers. Records that are missing either a date of immunization or date of birth will be recorded to help determine how many children were not vaccinated at that facility or lack complete records. Data collectors will continue working backwards through the registers entering data for every Xth child (according to the sampling interval) until they have successfully recorded the date of birth and date(s) of immunization for 30 children.

At end line:

The end line registry extraction will utilize the same sampling technique as baseline. The same sample size (N = 30) will be used with the sampling period being the duration of the study period. As there will be children who may not receive their birth dose vaccines before the end line data collection, this indicator will focus on those children who did/did not receive the vaccine within 24 hours.

Contingency plan:

In the event of worsening COVID-19 transmission, facility staff will locate the relevant registry pages and will send photo records of the pages to study staff. Study staff will then continue with data extraction as outlined.

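### A 12-month baseline average is set against a 12 to 16 week end line window with no check of vaccination timeliness over time, so a change already under way would enter the reported change unseen

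*Combined protocol and SAP*

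**What the plan says.** Section 2.4 defines the child population as babies seen "during the 1-year baseline period and the intervention period". Under Section 2.9.1 the baseline sampling interval comes from "taking the total number of children entered into the immunization register for the previous 12 months", divided by 30, and the birth register is sampled the same way. The stated aim is "to ensure children are sampled throughout the entire year". End line uses the same technique and the same 30 per facility, "with the sampling period being the duration of the study period".

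Section 2.11 compares the facility-level value at baseline with that at end line. It calls all outcomes descriptive, but the intent is to assess preliminary impact. The one time series it plans is of births: "we will use the information contained in the DHIS2 over the last 2 years to compare historical yearly birth trends". Its stated purpose is to look for COVID-19 effects on in-facility births. Pandemic-related factors such as stock outs are noted informally at check-ins, which Section 2.8 places in the 12-week intervention.

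Section 2.14 covers purposive sampling, lack of statistical precision and register quality. It mentions neither trends over time nor the lack of a comparison group.

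**The concern.** All 15 facilities receive the intervention, so the baseline year is the only evidence of what would have happened without it. Collapsing the year to one average discards its time course. If timeliness was already rising, the average lies below the level just before training and the reported change is too large. If it was falling, the change is too small. Birth counts can be flat in either case.

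The 24-hour proportion is the primary outcome (Section 2.10), and the results are meant to inform preparation for the hepatitis B birth dose (Section 2.13). The dates needed to look at the time course are already being extracted.

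**Working it through.** **Inputs from the documents.** 15 facilities; 30 records per facility, per register, per round (no derivation is given, so 30 cannot be reproduced); baseline of 12 months; training in week 5 and end line extraction in week 17 (Section 5.4); 2019 timeliness, in other facilities, of 4% for BCG and 7% for OPV0 (Section 1.1). The plan's own interval examples are correct: 90/30 = 3, 30/30 = 1, 300/30 = 10.

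**Assumptions.** The slopes, vaccination delays and design effect below are illustrative and do not come from the documents.

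**1. Distance between windows.** The baseline midpoint is 26 weeks before study start. The end line midpoint is week 10 if the window is weeks 5–16 (the intervention), or week 8 if it is weeks 1–16 (study start to extraction). The gap is 26 + 10 = 36 or 26 + 8 = 34 weeks. At 52/12 = 4.33 weeks per month, that is 8.3 or 7.8 months.

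**2. Change produced by a linear trend alone** (slope × gap):

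| Assumed slope, points/month | Against full year | Against last 13 baseline weeks |
|---|---|---|
| 0.25 | 2.0–2.1 | 0.8–1.0 |
| 0.5 | 3.9–4.2 | 1.7–1.9 |
| 1 | 7.8–8.3 | 3.3–3.8 |
| 2 | 15.7–16.6 | 6.7–7.6 |

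The last column uses gaps of 6.5 + 8 = 14.5 and 6.5 + 10 = 16.5 weeks. The recent comparator more than halves the bias but does not remove it.

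**3. Pre-training weeks inside the end line window.** Read literally, the study period includes the four weeks before training: 4/16 = 25% of weeks 1–16. Those weeks would dilute any effect.

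**4. What the dates can show.** Baseline records: 15 × 30 = 450, or 450/4 = 112.5 per quarter pooled, but 30/12 = 2.5 per facility per month. Approximate 95% half-widths, ignoring clustering:
- Difference between two quarters at 7%: 1.96 × √(2 × 0.07 × 0.93/112.5) = 6.7 points.
- The same at 15%: 1.96 × √(2 × 0.15 × 0.85/112.5) = 9.3 points.
- End line (450) minus last quarter (112.5), both at 7%: 1.96 × √(0.07 × 0.93 × (1/112.5 + 1/450)) = 5.3 points.
- End line minus full year (450 each), both at 7%: 1.96 × √(2 × 0.07 × 0.93/450) = 3.3 points.

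Power to detect a rise from first to last baseline quarter (two-proportion test, two-sided 5%):

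| Rise | No clustering | Assumed design effect 2 |
|---|---|---|
| 4% to 10% | 0.42 | 0.24 |
| 4% to 15% | 0.81 | 0.51 |
| 4% to 20% | 0.96 | 0.75 |

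**5. Why the denominator matters.** Section 2.9.1 counts baseline records toward 30 only when both dates are present. Recent births not yet vaccinated drop out, leaving the early-vaccinated. Suppose true timeliness is constant at 7% and the other delays are exponential with mean m weeks. For births in the last 13 weeks, the share of late vaccinations already given is F = 1 − (m/13)(1 − e^(−13/m)), and the observed timely proportion is 0.07/(0.07 + 0.93F):
- m = 4: F = 0.704, observed 9.7%
- m = 6: F = 0.591, observed 11.3%
- m = 8: F = 0.506, observed 13.0%

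The two earliest quarters stay at 7.0–7.1%. A table restricted to records with both dates would thus show a rise of up to 6 points where none exists.

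**The case against.** The plan is openly descriptive, disclaims significance and centres on feasibility. The birth-count check is not presented as a check on timeliness. Section 2.5 excludes facilities in research or interventions that would affect the outcomes, which removes one obvious source of a prior rise. With 450 × 0.04 / 4 = 4.5 to 450 × 0.07 / 4 = 7.9 timely records expected per quarter, noise will dominate small movements. A careless table by quarter of birth could create a trend, as step 5 shows.

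The points on precision and denominators stand, and they shape the remedy. The descriptive label does not dispose of the matter: a descriptive change is still reported as preliminary impact, and its baseline should be the relevant one. The check-in notes do not reach back into the baseline year.

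Three stronger readings are tempting and are not supported:
- **That end line covers only a few weeks.** Only the data collection is short. The records sampled span the study period, about 12 to 16 weeks.
- **That the extracted dates would reveal any prior trend.** They can show only large shifts, and only with facilities pooled.
- **That the comparison should move to the last quarter whenever the baseline quarters appear to trend.** That rule has no criterion, and noise would often choose the comparator.

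**Conclusion.** The concern holds in limited form. The planned comparison cannot separate the intervention from a change in timeliness already under way, and no planned analysis looks for one. Under assumed linear trends of 0.5 to 1 point per month, the reported change would include about 4 to 8 points of pre-existing drift, similar in size to the 4% and 7% seen in 2019. A falling trend would bias the change by the same amount the other way.

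A reader might infer that timeliness was in fact changing, or that a reported gain would be spurious. The documents contain no evidence of either. The defect is that the plan does not look, although a rough look costs almost nothing. The half-widths assume 450 independent records per round; clustering by facility would widen them.

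**What to change.** **Section 2.11.** Add one descriptive table, all 15 facilities combined, of the 24-hour proportion for each vaccine by quarter of birth over the baseline year and by month after training.
- **Denominator:** every birth-register record sampled, with births lacking a vaccination date counted as not vaccinated within 24 hours. Section 2.9.1 already has these records noted. Use the same denominator at baseline and end line.
- **Comparators:** always report the end line change against both the full baseline year and the last baseline quarter, with the same calendar months a year earlier as context. Do not let the data choose between them.
- **Age at vaccination:** tabulate by quarter of vaccination, because recent births can only show young ages.
- **Birth counts:** keep the existing check as context.

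**Section 2.9.1.** Start the end line sampling window after training.

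**Section 2.14.** Add trends over time and the lack of a comparison group.

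**Cost.** One table from dates already extracted, a clarified window and a sentence or two of limitations. The last-quarter comparison is less precise (about ±5.3 points against ±3.3 for the full year, at 7% before clustering), and differences between quarters carry about ±7. Because Section 2.7.1 also changes how birth doses are recorded, counting undated births as not timely could make better recording look like better timeliness. The table should therefore give the number of undated records in each period.

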2.12 Data Quality Control Measures and Security

All surveys will be completed in an electronic format using a tablet with incorporated skip patterns to confirm the highest quality data. All data to be stored on a secure server and accessed only by the study team. To minimize data collection errors, daily supervision of data entry into the tablets will be reviewed.

2.13 Dissemination

Upon the completion of this study, the primary dissemination aim is to provide information that is valuable to the RDPH, EPI, NITAG, Department of Family Health -, and implementing partners for purposes of improving early coverage of birth dose vaccines and preparing for a potential HepB-BD introduction. The design of the evaluation, methods used to collect and analyze data, and results will be synthesized with input from the co-investigators into a technical report, which will be presented and shared with relevant stakeholders. With approval from MOPH, the key findings, lessons learned and recommendations resulting

from this feasibility assessment will also be shared more broadly with the global health community to inform the delivery of birth dose services in other countries.

2.14 Limitations

This pilot study will have several key limitations. The sample of the study will be small and purposeful in that it will only include 15 health facilities that meet a set of pre-defined criteria (see above). Therefore, this work will not be statistically precise nor be nationally representative and the participating sites will likely not experience certain challenges pertaining to birth vaccines that are undoubtedly experienced elsewhere in Cameroon as a whole (such as sites located in conflict zones, etc.). Instead, the purpose of the sample is to assess the feasibility of integration of birth dose vaccines BCG and OPV0 in maternity and newborn care services to gather lessons and formulate recommendations for the broader routine immunization and maternal and child health programs.

Data collected from registers to determine timing of vaccine administration results is a limitation in that it requires us to have both a date of birth and date of vaccination in facility registers. Therefore, babies who were born out of the facility (either at home or in a different facility) will not contribute to the aggregated figures, the same goes for babies who were born in the health facilities but receive vaccination elsewhere. Furthermore, we cannot guarantee the accuracy of the facility records. Key barriers and factors associated with the birth dose process will be descriptive in nature.

3 COVID-19 Impacts

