This was a cross-sectional study of 30 selected sites with both an immunization and labor and delivery unit across three regions (Center, Far North, and West) within Cameroon, utilizing both qualitative and quantitative approaches. The findings from the study indicate that across the 30 sites, only 4% and 7% of newborn received BCG and OPV0, respectively, within 24 hours. The reported key barriers hindering timely birth dose administration included: (i)maternity units were not equipped functioning fridges, (ii) lack of awareness and insufficient demand by caregivers for birth dose vaccines (e.g. birth dose education at antenatal visits, (iii)vaccine hesitancy among caregivers mainly due to religious beliefs, myths and rumors. The key facilitators were (i) raising awareness among caregivers on the importance of birth dose vaccinations, (ii) improving access to functioning fridges in the maternity unit and (ii) addressing practices on multidose vial policies.

Attaining high timely coverage with birth dose vaccines is a common challenge among low- and middleincome countries. This challenge has been attributed to numerous barriers including, lack of integration into maternal and newborn health programs and protocols, lack of healthcare worker and caregiver knowledge, unavailability of cold chain storage, fear of vaccine wastage for multi-dose vials, high proportions of out of facility births, and difficulties of access and demand for target cohort.^{6,7,8,9} These barriers echo those identified in 2019 in Cameroon Global best practices and lessons learned from other countries suggest that successful timely administration of the birth dose vaccines relies on many system components including integrated processes between maternity and immunization units, healthcare worker awareness of birth dose administration guidelines, and demand from mothers and community.

⁶ WHO. Practices to improve coverage of the hepatitis B birth dose vaccine, January 2013.

⁷ Miyahara, R., Jasseh, M., Gomez, P., Shimakawa, Y., Greenwood, B., Keita, K., Ceesay, S., D'Alessandro, U., & Roca, A. (2016). Barriers to timely administration of birth dose vaccines in The Gambia, West Africa. *Vaccine*, *34*(29), 3335–3341. https://doi.org/10.1016/j.vaccine.2016.05.017

⁸ Gavi the Vaccine Alliance, Annex C: Hepatitis B Birth Dose Investment Case. October 2018.

⁹ Country presentations at WHO AFRO regional workshop on Hepatitis B birth dose, June 2019.

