1.2 Study Aim and Objectives

The main aim of the pilot study aim is to assess the feasibility of immunizing newborns, within selected facilities, with BCG and OPV0 within 24 hours of birth by integrating routine immunization into maternity and early newborn care. In this study only the current birth vaccines (BCG and OPV) will be assessed. The findings will inform strategies for strengthening the birth platform as well as HepB-BD introduction which is envisaged in the cMYP (2016-2021).

Further, the specific objectives of this pilot study are to:

- 1. Integrate birth dose immunizations into facility-based maternity services
- 2. Measure the change in proportion of facility births receiving birth doses BCG and OPV0 within 24 hours
- 3. Measure the change in average age of all babies receiving birth doses of BCG and/or OPV0 at the facility
- 4. Assess the operational feasibility and acceptability of interventions and describe any factors (barriers and enablers) that may influence further implementation of birth dose strategies

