1.3 Justification for Pilot Study

Cameroon's national policy recommends that OPV0 and BCG be administered as soon as possible after birth. While coverage rates for BCG (84%) and OPV0 (79%)¹⁰ are relatively high in Cameroon, it is estimated that these vaccines are often administered weeks or months after birth,¹¹ not within the timeframe recommended for their administration or that which will be needed for a successful HepB-BD program (<24 hours after birth).¹² Currently, most health facilities do not administer vaccines every day, but rather only on designated immunization days. With babies being born every day, this poses a challenge to reach newborns via the current immunization service delivery system. Based on the study conducted in 2019 that highlighted the barriers and facilitators of timely birth dose administration, the Ministry of Public Health with support of CHAI decided to pilot facility specific HepB BD integration programs. A component that arose from the 2019 study that was of key concern was the lack of communication and integration between the immunization and maternity wards. Thus, this pilot work proposes a facility-based approach to better integrate birth dose vaccination into the broader facility-based maternity and newborn care processes to ensure newborns born within facilities are vaccinated within the recommended timeframe. While the previous assessment and studies have identified many common barriers to timely birth dose administration, the purpose of this work is to focus on the feasibility of integrating the birth dose vaccine process into maternity practices.

¹⁰ EPI administrative data 2018

¹¹ Chiabi A., Nguefack F., Njapndounke F., Kobela M, Kenfack K, Nguifack S., Mah E, Nguefac-Tsague G., Angwafo F., (2017). Vaccination of infants aged 0 to 11 months at the Yaounde Gynaeco-obstetric and pediatric hospital in Cameroon: how complete and how timely?. *BMC Pediatrics*. 2017. 17:206. DOI 10.1186/s12887-017-0954-1

¹² WHO (2015). A Guide for Introducing and Strengthening HepB-BD Vaccination. www.who.int/immunization/documents

2 Methodology

[figure not shown]

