Roles and responsibilities of different providers	Outline detailed roles and responsibility for each HCW involved in birth dose vaccinations. Develop and train on facility-specific work flows (see section 2.5 above) which will orient HCW to how the birth dose administration fits into maternal and newborn care in terms of sequencing of services, process for recording and reporting and collecting the vaccines (see below), and mitigation plans and reminders (e.g. to follow safe newborn checklist and best practices in terms of handling emergencies first, etc.)		
Policy for birth dose administration	Provide information on updated policy for the birth dose vaccines to be administered in the maternity unit.		
Cold chain storage planning	During the baseline assessment, study members will assess each maternity unit's 24/7 access to a working refrigerator for vaccine storage. Each facility will have a plan (as part of the integrated workflow) on how to access the vaccines immediately after a birth takes place and will be outlined. For facilities without cold chain equipment, a daily schedule (including weekends and holidays) will be implemented where a morning trip is		
	made to the closest health facility or district health service with CCE to pick up vaccines and an evening trip is done to return unused vaccines to the same health facility.		
Recording and reporting harmonization	To ensure birth doses vaccines are properly recorded in both facility records and for the purposes of this pilot study, two record changes will take place and will be described in detail.		
	Birth dose maternity reporting form For the duration of the pilot study maternity units will be provided with a simple recording form with space to document each birth and information on birth doses given. Scenarios for accurately filling out the form will be discussed.		
	Updated birth registry		

	The birth registry will also be updated to include a column to check if the baby received the birth doses of BCG and OPV0 within 24 hours. At the end of each day, this paper will be brought to the EPI unit to incorporate into their record books. In addition, child health cards will need to be stored in maternity units so caregivers can acquire the book at the time of the birth dose administration, and the updated birth dose information is recorded on the health card.

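### The change in average age mixes earlier dosing with a change in which facility births are captured; section 2.14 discloses the exclusion but not that it differs between rounds

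*Combined protocol and SAP*

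**What the plan says.** Objective 3 in section 1.2 is to "Measure the change in average age of all babies receiving birth doses of BCG and/or OPV0 at the facility". Section 2.9.1 takes the figure from the immunization register: "Data extraction for children in the immunization register will occur by using a sampling interval", continued until 30 children per facility have both a birth date and a dose date. Records lacking either date are noted but "will not count towards the total desired sample size for timeliness coverage". End line uses the same method and sample size over the study period.

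Section 2.14 explains that using the registers is a limitation because "it requires us to have both a date of birth and date of vaccination in facility registers". Babies born outside the facility are therefore left out, and "the same goes for babies who were born in the health facilities but receive vaccination elsewhere".

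Two passages describe how doses are given before the intervention. Section 1.3: "Currently, most health facilities do not administer vaccines every day, but rather only on designated immunization days". Section 1.1, on the 2019 study: "only 4% and 7% of newborn received BCG and OPV0, respectively, within 24 hours". Under the intervention, Table 4 in section 2.7.1 has maternity doses recorded on paper each day, and "this paper will be brought to the EPI unit to incorporate into their record books".

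Table 5 in section 2.10 lists average age as a key indicator at baseline and end line, and section 2.11 compares the two facility by facility. The declared primary outcome is the 24-hour proportion, and all analysis is descriptive.

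**The concern.** At baseline few babies are dosed in the first 24 hours, so nearly every facility birth in the immunization register is there because the family came back to the same facility. Families who went elsewhere are absent.

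At end line a baby dosed in maternity enters the register at age 0 once the paper is transferred, whether or not the family would have returned. A baby missed in maternity still enters only on return. The group being averaged therefore changes between rounds, and the intervention causes the change. Section 2.14 describes the loss as though it were the same in both.

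The average can then fall even if no returning baby is vaccinated earlier. The results go to the national programme and advisory group to inform a hepatitis B birth-dose introduction (section 2.13). A reader there would naturally take a fall in average age as earlier vaccination of the same population.

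**Working it through.** The plan gives no average age, return rate or expected fall, so there is no figure of its own to reproduce. A simple mixture model shows the size of the effect.

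**Inputs**
- p: share of facility births dosed on day 0 at the facility. The baseline proxy is 5.5%, the midpoint of the 4% (BCG) and 7% (OPV0) in section 1.1. Those figures come from the 2019 sites, which section 2.5 excludes from this study. End-line values are assumed.
- r: share of the remaining births who return to the same facility. Assumed, 0.3 to 0.9.
- L: mean age at late facility doses. Assumed, 20 days. It cancels from the ratios.
- k: mean age at doses given elsewhere, divided by L. Assumed; k = 1 first.

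**Formulas**
- Register mean = (1−p)rL / (p + (1−p)r).
- Mean over all facility births, dosed anywhere = (1−p)(r + (1−r)k)L. With k = 1 this is (1−p)L.

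**Results with k = 1 and p rising from 5.5% to 40%.** The fall over all births is (0.40 − 0.055) × 20 = 6.9 days.

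| r | Register mean, baseline | Register mean, end line | Register fall | Ratio to 6.9 |
|---|---|---|---|---|
| 0.3 | 16.75 | 6.21 | 10.5 | 1.53 |
| 0.5 | 17.91 | 8.57 | 9.3 | 1.35 |
| 0.7 | 18.46 | 10.24 | 8.2 | 1.19 |
| 0.9 | 18.79 | 11.49 | 7.3 | 1.06 |

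For r = 0.5, for example, the baseline mean is 0.945 × 0.5 × 20 / (0.055 + 0.4725) = 17.91.

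The ratio shrinks as p grows. With p reaching 50% (fall over all births 8.9 days) it is 1.36, 1.26, 1.15 and 1.05 for the same four r. With p reaching 70% and r = 0.9 it is 1.02.

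**Composition alone.** Suppose no returning baby is dosed earlier, and half of the non-returners are newly dosed on day 0. The register mean is multiplied by r / (r + 0.5(1−r)). It falls by 33%, 18% or 5% for r = 0.5, 0.7 or 0.9.

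**What can change the sign**
- *Age at doses elsewhere.* With baseline p = 4%, r from 0.5 to 0.9 and end-line p from 0.3 to 0.8, the register fall equals the all-births fall at k between 1.14 and 1.96. Above that point the fall is understated; at k = 2 the ratio is 0.71 to 0.99.
- *Transfer to the EPI register.* If a share t of maternity doses is transferred, the end-line mean is (1−p)rL / (pt + (1−p)r). Take r = 0.7, k = 1 and p rising from 4% to 50%. The all-births fall is 0.460L. The register fall is 0.532L at t = 1, 0.477L at t = 0.8 and 0.405L at t = 0.6, with break-even near t = 0.75.

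**Scope.** The model covers facility births. Section 2.4 includes all babies received in the EPI unit, while section 2.14 says births outside the facility will not contribute. If outside births do enter the average, new day-0 doses dilute them, which adds to the apparent fall.

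**The case against.** **The register measures what Objective 3 asks.** The objective concerns babies dosed at the facility, and the register average is on target for that group. This stands. The fault lies in reading the change as earlier dosing of the same babies, which the plan does not warn against.

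**The direction is not assured.** A reader might infer that the bias always favours the intervention, or that every maternity dose reaches the register. The documents support neither. They give no age for doses elsewhere and no return rate. Table 4 describes a daily paper transfer without stating its completeness, and section 2.14 does not guarantee the accuracy of records. This stands: overstatement is likely, not certain.

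**The end-line window may include the four baseline weeks, which shrinks the observed fall.** At r = 0.7 and p from 4% to 50%, with 4 of 16 weeks pre-intervention, the register fall drops from 0.532L to 0.416L, below 0.460L. But the window dilutes both sides. End-line p over the window is 0.25 × 0.04 + 0.75 × 0.50 = 0.385, so the all-births fall is 0.345L. The ratio is 0.416 / 0.345 = 1.21, so this objection fails.

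**The fix shares part of the problem.** The percentage dosed at this facility by day 28 also rises when babies shift from other sites. With p from 5.5% to 40%, r = 0.5 and all late doses given by day 28, it goes from 0.055 + 0.945 × 0.5 = 53% to 0.40 + 0.60 × 0.5 = 70%, with total vaccination unchanged. This stands and must be stated with the result. The denominator is at least the same kind of group in both rounds: all sampled facility births.

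**The indicator is secondary and descriptive, and the exclusion is disclosed.** True, and it limits the severity. Section 2.9.1 also counts sampled births with no dose date. But no passage links that count to the average age, and a descriptive change will still be reported and read.

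**Conclusion.** The concern holds as a problem of interpretation. The change in average age combines earlier dosing with a change in who is captured, and section 2.14 treats the loss as constant. The fall is likely overstated: by about 1.2 to 1.5 times for r from 0.7 to 0.3 with p reaching 40%, and by 1.02 to 1.06 times for r = 0.9 with p reaching 70% to 40%. These figures assume k = 1, complete transfer, and a baseline p borrowed from other sites. Size and sign cannot be settled from the documents: the fall could be understated if doses elsewhere come much later or if transfer is incomplete. The primary outcome is a different indicator, so this should be corrected but does not undermine the study.

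**What to change.** 1. For facility births, base the timing result on the birth-register sample in both rounds. Keep every sampled birth in the denominator, whether or not a dose date is found. This replaces the rule in section 2.9.1 of sampling until 30 children have both dates. The delivery register form in section 5.3 speaks of 30 children in total, so the two must be reconciled in any case.
2. Report, for each vaccine and round, the cumulative percentage with a dose recorded at this facility, in either register, by day 1, 7, 14 and 28 (Kaplan-Meier, censored at the extraction date). Say in the table title that these are doses recorded at this facility, and in a note that day 7 to 28 values can also rise because babies shift from other sites.
3. Keep the immunization-register average age as a description of babies dosed at the facility. Show beside it the share of sampled births with a recorded facility dose in each round.
4. Add to section 2.14 that capture differs between rounds because of the intervention, that the effect on average age is of unknown size and sign, and that the change should not be read as earlier dosing of the same babies.

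Cost: no new data field, since the delivery register form already holds the birth date, the dose dates from both registers and whether the child was found. The changes are to the stopping rule, the data collectors' instructions and the analysis text. Fewer than 30 children per facility may then have a dose date, and babies dosed elsewhere will appear as having no dose recorded at this facility.
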